I. Dose Escalation Phase 1 Part of Study: The study will employ the standard “cohort of three” design (2). Three patients are treated at each dose level with expansion to six patients per cohort if DLT is observed in one of the three initially-enrolled patients at each dose level. If no DLT occurs after 2 doses, escalation to the next dose level will be permitted. The maximum tolerated dose is defined as the highest safely tolerated dose, where not more than one patient experienced DLT, with the next higher dose level having at least two patients who experienced DLT. Patients in the dose escalation study may continue treatment at their designated dose levels up to eighteen 3-week cycles or until significant disease progression or unacceptable toxicity occurs. No intra-patient dose escalation will take place.

Dose of nivolumab: 3 mg/kg IV over 30 min. q 3 weeks (Day 1 of every 21-day cycle)

Dose of ABI-009:

NB: ABI-009 will start after 2nd nivolumab dose and will be administered on D8 and D15 beginning in C2.

Escalating doses IV over 30 min for 2 of every 3 weeks:

Treatment Cycle	# Pts.	Dose Level	Dose, mg/m ²
Every 3 weeks	3-6	I	56
Every 3 weeks	3-6	II	75
Every 3 weeks	3-6	III	100

Note: DLT includes any \geq Grade 3 colitis, hepatitis, or pneumonitis, any Grade 1-2 colitis, hepatitis or pneumonitis that recurs, worsens or persists with oral steroids longer than 14 days, symptoms of adrenal crisis, any Grade 4 hematologic toxicity or any \geq Grade 3 non-hematologic toxicity. If DLT develops in more than 1 patient at Dose 56 mg/m², the dose will be de-escalated to 45 mg/m² and to 30 mg/m² if DLT develops at 45 mg/m².

II. Expansion Phase 2 Part of Study: Following dose escalation, an additional 22-28 patients will receive ABI-009 at the MTD and defined doses of nivolumab to assess overall safety and potential efficacy in a greater number of patients. Patients in the expansion phase of the study may continue treatment up to 18 3-week treatment cycles or until significant disease progression or unacceptable toxicity occurs.

The study will be conducted in compliance with International Conference on Harmonisation (ICH) Good Clinical Practices (GCPs).

Surgical Resection: After three or more treatment cycles, the principal investigator may recommend surgical debulking, complete surgical removal or a biopsy. If residual disease

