Follow-up period is the on-study time period after the EOT Visit. All patients that discontinue study drug and have not withdrawn full consent to participate in the study will continue in the follow-up phase for survival and initiation anticancer therapy. Follow up will continue approximately every 12 weeks (+/- 3 weeks), until death, withdrawal of consent, or the study closes, whichever is the earliest. This evaluation may be made by record review and/or telephone contact.

Study Treatment

Patients will receive nivolumab 3 mg/kg as IV infusion over 30 min every 3 weeks (Day 1 of every 21-day cycle), followed by escalating doses of ABI-009 30, 45, 75 mg/m² for 2 of every 3 weeks by IV infusion over 30 minutes. ABI-009 dosing will start after 2nd nivolumab dose and to be administered on Day 8 and Day 15 of every cycle beginning in Cycle 2. Patients will continue therapy until unequivocal clinical disease progression, unacceptable toxicity, or until in the opinion of the investigator the patient is no longer benefiting from therapy, or at the patient's discretion.

Overview of Key Safety Assessments

Safety and tolerability will be monitored through continuous reporting of treatment-emergent and treatment-related adverse events (AEs), AEs of special interest, laboratory abnormalities, and incidence of patients experiencing dose modifications, dose delay/dose not given, dose interruptions, and/or premature discontinuation of IP due to an AE. All AEs will be recorded by the investigator from the time the patient signs informed consent until 28 days after the last dose of IP. Adverse events will be graded by National Cancer Institute (NCI) Common Terminology Criteria for Adverse Events (CTCAE) v4.03.

Physical examination, vital signs, laboratory assessments (e.g., serum chemistry, hematology), and ECOG performance status will be monitored. All SAEs (regardless of relationship to IP) will be followed until resolution. Local laboratory analysis will be performed as per study schedule.

The MTD for ABI-009 will be determined, and will be used in the Phase 2 part of the study.

Overview of Key Efficacy Assessments

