1.4. Rationale for the Schedule of the Study

In this study nivolumab will be given once every 3 weeks (D1 of a 3 week cycle) and ABI-009 will be administered on D8 and D15 of the 3 week cycle starting in Cycle 2 (C2). Thus, ABI-009 will be given weekly for 2 weeks with a 1 week break.

Although nivolumab is approved on a biweekly schedule, in this study, because nivolumab is being given in combination with ABI-009 which is administered 2 out of 3 weeks, a 3 weekly schedule for nivolumab was adopted. In a prior Phase 3 combination study with ipilimumab, nivolumab 3 mg/kg was given every 3 weeks during the time when combination therapy was given (65). In this study, nivolumab and ABI-009 have different mechanisms of action. Therefore, it is not expected that the individual toxicities would significantly overlap. As a safety precaution, nivolumab will be given every three weeks (instead of every 2 weeks) when used in combination with ABI-009. Additionally, escalating doses of ABI-009 will start two dose levels below the MTD of 100 mg/m² observed in the Phase 1 study (44), as well as a de-escalation schedule if DLT is noted at Dose Level 1 (See Dose Reduction in [Section 6](#)).

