2.3. Study Design

This is an open label, dose-seeking phase 1/2 study using a defined dose of nivolumab and escalating doses of ABI-009 given intravenously.

I. Dose Escalation Phase 1 Part of Study: The study will employ the standard "cohort of three" design (Storer, 1989). Three patients are treated at each dose level with expansion to six patients per cohort if DLT is observed in one of the three initially-enrolled patients at each dose level. If no DLT occurs after 2 doses, escalation to the next dose level will be permitted. The maximum tolerated dose is defined as the highest safely tolerated dose, where not more than one patient experienced DLT, with the next higher dose level having at least two patients who experienced DLT. Patients in the dose escalation study may continue treatment at their designated dose levels up to eighteen 3-week treatment cycles or until significant disease progression or unacceptable toxicity occurs. No intra-patient dose escalation will take place.

Dose of nivolumab: 3 mg/kg IV over 30 min. q 3 weeks

NB: ABI-009 will start after 2nd Nivo dose, and will be administered on D8 and D15 beginning in C2.

Dose of ABI-009: Escalating doses IV over 30 min for 2 of every 3 weeks:

Treatment Cycle	# Pts.	Dose Level	Dose, mg/m2
Every 3 weeks	3-6	I	56
Every 3 weeks	3-6	II	75
Every 3 weeks	3-6	III	100

Note: DLT includes any \geq Grade 3 colitis, hepatitis, or pneumonitis, any Grade 1-2 colitis, hepatitis or pneumonitis that recurs, worsens or persists with oral steroids longer than 14 days, symptoms of adrenal crisis, any Grade 4 hematologic toxicity or any \geq Grade 3 non-hematologic toxicity.

II. Expansion Phase 2 Part of Study: Following dose escalation, an additional 22-28 patients will receive ABI-009 at the MTD and defined doses of nivolumab to assess overall safety and potential efficacy in a greater number of patients. Patients in the expansion

phase of the study may continue treatment up to 18 3-week treatment cycles or until significant disease progression or unacceptable toxicity occurs.

The study will be conducted in compliance with International Conference on Harmonisation (ICH) Good Clinical Practices (GCPs).

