6. DESCRIPTION OF STUDY TREATMENTS (ABI-009/NIVO)

6.1. ABI-009/Nivolumab Dosage, Administration, and Schedule

For the Phase 1 part of study, patients will receive nivolumab 3 mg/kg as IV infusion over 60 min every 3 weeks, followed by escalating doses of ABI-009 56, 75, 100 mg/m² for 2 of every 3 weeks by IV infusion over 30 minutes. ABI-009 will start on Day 8 of Cycle 2. If DLT develops in more than 1 patient at Dose 56 mg/m², the dose will be de-escalated to 45 mg/m² and to 30 mg/m² if DLT develops at 45 mg/m². Patients will continue therapy until unequivocal clinical disease progression, unacceptable toxicity, or until in the opinion of the investigator the patient is no longer benefiting from therapy, or at the patient's discretion.

For the Phase 2 part of study, patients will receive nivolumab 3 mg/kg as IV infusion over 30 min every 3 weeks, followed by ABI-009 at the MTD dose for 2 of every 3 weeks by IV infusion over 30 minutes. ABI-009 will start on Day 8 of Cycle 2. Patients will continue therapy until unequivocal clinical disease progression, unacceptable toxicity, or until in the opinion of the investigator the patient is no longer benefiting from therapy, or at the patient's discretion.

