In the event of clinically significant AE in any part of the study, treatment may be withheld and supportive therapy administered as clinically indicated. If the toxicity or event is not grade 3/4 and resolves to baseline or grade 1 in less than or equal to 14 days of stopping therapy, then treatment may be restarted. Dose reduction of ABI-009 should be considered as clinically indicated.

If the toxicity does not resolve to at least grade 1 in less than 14 days, withdrawal from treatment with the IP is recommended. However, if the investigator and AADI Medical Monitor agree that further treatment would benefit the patient, treatment can continue with at least one dose level dose reduction, per Table 4.

Table 4. Dose Level Reduction Guidelines

Dose level	ABI-009 Dose/Schedule
1	Initial Dose: 56 mg/m ²
-1 (first dose reduction)	45 mg/m ²
-2 (second dose reduction)	30 mg/m ²

If an AE resolves to grade 1 or baseline at the reduced dose level, and no additional toxicities are seen during the following cycle of study treatment at the reduced dose, the dose may be increased to the previous dose level.

Any patient meeting the criteria for Hy's Law case (i.e. severe drug-induced liver injury) will be considered a dose-limiting toxicity. A Hy's Law case is defined as: AST or ALT values of $\geq 3 \times$ ULN AND with serum total bilirubin level (TBL) of $> 2 \times$ ULN without signs of cholestasis and with no other clear alternative reason to explain the observed liver-related laboratory abnormalities.

ABI-009 dose modification guidelines are outlined in Table 4 and Table 5

for clinically significant toxicities that are deemed related. The dosing schedule is described in the Schedule of Assessments, Table 2.

Table 5. Dose Modification Algorithms for Adverse Events Possibly Related to ABI-009

System/Organ	Adverse Event	CTCAE Grade v4.03	Dose modification Algorithm
Mucosa	Stomatitis, mucosal inflammation	Grade 2	Hold ABI-009 until resolution to Grade 1 or baseline and restart at the same dose for 1 st occurrence; for subsequent occurrences, drug will be restarted at a reduced dose; provide supportive care as clinically indicated.
		Grade ≥3	Hold ABI-009 until resolution to Grade 1 or baseline and restart at the same dose for 1 st occurrence for subsequent occurrences, drug will be restarted at a reduced dose; provide supportive care as clinically indicated.

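### The synopsis lists escalating ABI-009 doses of 30, 45, 75 mg/m², but its own dose table, Section 2.3 and Section 6.1 list 56, 75, 100

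*Combined protocol and SAP*

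**What the plan says.** **The two lists.** The synopsis paragraph headed Study Treatment describes nivolumab "followed by escalating doses of ABI-009 30, 45, 75 mg/m² for 2 of every 3 weeks by IV infusion over 30 minutes". Section 6.1, in almost the same sentence for the Phase 1 part, says "followed by escalating doses of ABI-009 56, 75, 100 mg/m² for 2 of every 3 weeks by IV infusion over 30 minutes". The Study Design part of the synopsis and Section 2.3 each carry a table with Levels I, II and III at 56, 75 and 100 mg/m² and 3-6 patients per level. In Section 2.3 that table stands under the line "Dose of ABI-009: Escalating doses IV over 30 min for 2 of every 3 weeks".

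**Rules that refer to the levels.**
- De-escalation (note to the synopsis table, and Section 6.1): "If DLT develops in more than 1 patient at Dose 56 mg/m², the dose will be de-escalated to 45 mg/m²", with a further step to 30 mg/m² if DLT occurs at 45.
- MTD (synopsis and Section 2.3): the highest dose at which no more than one patient had a DLT, "with the next higher dose level having at least two patients who experienced DLT".
- Starting level (Section 1.4): "escalating doses of ABI-009 will start two dose levels below the MTD of 100 mg/m² observed in the Phase 1 study", "as well as a de-escalation schedule if DLT is noted at Dose Level 1".
- Dose reduction (Section 6.2.1, Table 4): the first row reads "Initial Dose: 56" mg/m², with 45 and 30 as the first and second reductions. The Phase 2 text above it plans for the case in which the MTD is 56.

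**Related wording.** Section 6.2.1 sets neutrophil, platelet and hemoglobin requirements before ABI-009 on Day 1 of each cycle, although ABI-009 is scheduled only on Days 8 and 15 from Cycle 2. Nivolumab is infused over 60 minutes in Section 6.1 (Phase 1) and Section 7.5. It is infused over 30 minutes in both synopsis passages, Section 2.3 and Section 6.1 (Phase 2).

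**The concern.** In a dose-finding trial the list of levels is part of the definition of the primary endpoint. It fixes the dose given to the first cohort, the highest dose that can be tested, and the doses that can be named as the MTD. The MTD is then carried into Phase 2. A plan with two lists leaves all of these open.

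The synopsis also contradicts itself: its Study Design table and its Study Treatment sentence disagree. The Study Treatment sentence cannot be read as a description of the de-escalation steps. It calls its doses escalating, includes 75, and omits both 56 and 100.

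**Working it through.** **1. The texts side by side**

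| Place | Doses (mg/m²) | Role given to them |
|---|---|---|
| Synopsis, Study Treatment | 30, 45, 75 | escalating doses |
| Synopsis, Study Design table | 56, 75, 100 | Levels I-III |
| Section 2.3 table | 56, 75, 100 | Levels I-III |
| Section 6.1, Phase 1 | 56, 75, 100 | escalating doses |
| Synopsis table note; Section 6.1 | 45, then 30 | de-escalation after DLT at 56 |
| Section 6.2.1 and Table 4 | 56, then 45, then 30 | initial dose, then reductions |

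This is not a table-extraction fault, because both lists also appear in running prose.

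**2. Size of the difference.** Call the Study Treatment list A = {30, 45, 75} and the other B = {56, 75, 100}.
- Distinct doses across the two: {30, 45, 56, 75, 100}, five in all.
- Doses in both: {75}. It is the third dose in A and the second level in B.
- First dose: 56/30 = 1.87.
- Top dose: 100/75 = 1.33.

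**3. Which doses can be declared the MTD.** Taken literally, the definition needs a higher level that can show at least two patients with DLT, so the top level of a list is not eligible.

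| Reading | List A | List B |
|---|---|---|
| Literal definition, escalation levels only | {30, 45} | {56, 75} |
| Literal, plus the stated de-escalation to 45 and 30 | {30, 45} | {30, 45, 56, 75} |
| As above, and a tolerated top level may be the MTD | {30, 45, 75} | {30, 45, 56, 75, 100} |

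Under the first reading the sets do not overlap. Under the second they share 30 and 45, but under list B those doses are reached only after DLT in more than one patient at 56. In all three readings 56 is a candidate under B and not under A.

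**4. De-escalation.** The trigger is tied to 56, which is not in list A. If A applied, Dose Level 1 would be 30, and the plan states no ABI-009 level below 30, although Section 1.4 refers to a de-escalation schedule from Dose Level 1.

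**5. Does Table 1 settle it?** For three patients, expanded to six after one DLT, the probability of escalating at DLT rate p is (1-p)³ + 3p(1-p)² × (1-p)³.

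| p | Calculated | Table 1 |
|---|---|---|
| 0.1 | 0.729 + 0.177 = 0.906 | 0.91 |
| 0.2 | 0.512 + 0.197 = 0.709 | 0.71 |
| 0.3 | 0.343 + 0.151 = 0.494 | 0.49 |
| 0.4 | 0.216 + 0.093 = 0.309 | 0.31 |
| 0.5 | 0.125 + 0.047 = 0.172 | 0.17 |

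Table 1 is reproduced. The formula contains no dose, so Table 1 neither resolves the conflict nor is altered by it.

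**The case against.** The strongest reply is that a single synopsis sentence is the outlier. The synopsis table, Section 2.3, Section 6.1, Table 4 and the Phase 2 reduction text agree with one another. Only the tables number the levels and give cohort sizes. The trial has one center, so sites cannot diverge in how they read it. This lowers the practical risk and makes the repair easy. It does not make the text consistent: nothing in the plan says that one section or the majority prevails, and a starting dose should not be left to inference.

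Three narrower objections have some force.
- **Section 1.4 is ambiguous.** Its 100 mg/m² is the MTD of the earlier single-agent study, whose levels in Section 1.2.4 were 45, 56.25, 100, 125 and 150. Two levels below 100 is 45 on that ladder and 56 on this trial's tables. Section 1.4 therefore cannot confirm the 56, 75, 100 list, but neither count gives a start at 30.
- **The candidate sets rest on assumptions.** They treat the Study Treatment sentence as a complete ladder. Also, the step from 45 to 30 has no patient count, so including 30 for list B under the literal definition assumes that at least two patients had DLT at 45. The result for 56 does not depend on that step.
- **The missing level below 30 is conditional.** It is a gap only if the Study Treatment list governs.

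**Conclusion.** The concern holds. The current text gives two incompatible escalation lists for the drug whose MTD is the primary endpoint, with first doses 1.87-fold apart, top doses 1.33-fold apart and one dose in common. The conflict rests on the wording alone. Only the comparison of candidate MTDs needs the assumptions stated with it. This must be fixed before the plan can be relied on for dose assignment or for declaring the MTD.

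That rating applies only to the dose lists. The Day 1 blood-count rule is a matter of unclear wording: it names a day with no scheduled ABI-009 dose, and the line that follows holds treatment without naming the drug. The heading of Section 6.2 points to ABI-009, and blood counts on Days 1, 8 and 15 together with the resume criteria in Table 5 give partial cover. The nivolumab infusion time, and the fact that Table 4 gives steps only from 56 mg/m², are minor.

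**What to change.** Reconcile both synopsis passages (Study Design and Study Treatment), Sections 1.4, 2.3 and 6.1, and Table 4 to one list of ABI-009 escalation and de-escalation levels. Check that the de-escalation trigger and the MTD definition refer to levels in that list. The sponsor decides which text is correct; this review takes no position on the dose.

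In the same revision:
- reconcile the day and the drug in the Section 6.2.1 blood-count rule with the dosing schedule, and state whether it is a start-of-cycle check or a check before each infusion;
- reconcile the nivolumab infusion time across the synopsis and Sections 2.3, 6.1 and 7.5;
- state the scope of Table 4.

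The cost is a clarification or amendment to the text, with the approvals that Section 11.4 requires for an amendment. It adds no visits or tests.

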In Trial 1, where patients were evaluated at baseline and during the trial for thyroid function, Grade 1 or 2 hypothyroidism occurred in 8% (21/268) of patients receiving nivolumab and none of the 102 patients receiving chemotherapy. The median time to onset was 2.5 months (range: 24 days-11.7 months). Seventeen of the 21 patients with hypothyroidism received levothyroxine. Fifteen of 17 patients received subsequent nivolumab dosing while continuing to receive levothyroxine.

Grade 1 or 2 hyperthyroidism occurred in 3% (8/268) of patients receiving nivolumab and 1% (1/102) of patients receiving chemotherapy. The median time to onset in nivolumab-treated patients was 1.6 months (range: 0-3.3 months). Four of five patients with Grade 1 hyperthyroidism and two of three patients with Grade 2 hyperthyroidism had documented resolution of hyperthyroidism; all three patients received medical management for Grade 2 hyperthyroidism.

- **Any other severe or Grade 3 treatment-related adverse reactions**

Other clinically significant immune-mediated adverse reactions can occur. Immune-mediated adverse reactions may occur after discontinuation of nivolumab therapy.

The following clinically significant, immune-mediated adverse reactions occurred in less than 1% of nivolumab-treated patients in Trial 1: pancreatitis, uveitis, demyelination, autoimmune neuropathy, adrenal insufficiency, and facial and abducens nerve paresis.

Across clinical trials of nivolumab administered at doses of 3 mg/kg and 10 mg/kg the following additional clinically significant, immune-mediated adverse reactions were identified: hypophysitis, diabetic ketoacidosis, hypopituitarism, Guillain-Barré syndrome, and myasthenic syndrome.

Nivolumab was discontinued for adverse reactions in 9% of patients. Twenty-six percent of patients receiving nivolumab had a drug delay for an adverse reaction. Serious adverse reactions occurred in 41% of patients receiving nivolumab. Grade 3 and 4 adverse reactions occurred in 42% of patients receiving nivolumab. The most frequent Grade 3 and 4 adverse reactions reported in 2% to less than 5% of patients receiving nivolumab were abdominal pain, hyponatremia, increased aspartate aminotransferase, and increased lipase. Other adverse events that occurred in $\geq 10\%$ of patients were rash, pruritus, cough, upper respiratory tract infection, peripheral edema, increased AST, increased alkaline phosphatase, hyponatremia, increased ALT, and hyperkalemia, with

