2.5. End of Study, End of Treatment, End of Treatment Visit, Follow-up Period

End of Study (EOS) is defined as either the date of the last visit of the last patient to complete the study, or the date of receipt of the last data point from the last patient that is required for primary, secondary, and/or exploratory analysis, as pre-specified in the protocol.

End of Treatment (EOT) is defined as the date of the last dose of ABI-009 or nivolumab for an individual patient

End of Treatment Visit for a patient is when safety assessments and procedures are performed after the last treatment, which must occur at least 4 weeks (\pm 7 days) after the last dose of ABI-009 or nivolumab.

Primary analysis for this study will occur after all patients have either completed the study or completed 12 months of treatment. Patients who are still active at the time of the primary analysis may continue on study until disease progression or medication intolerance is observed.

Primary Completion is the time when the last patient is assessed or receives an intervention for the purposes of final collection of data for the primary analysis.

Follow-up period is the on-study time period after the EOT Visit. All patients that discontinue study drug and have not withdrawn full consent to participate in the study will continue in the follow-up phase for survival and anticancer therapy. Follow-up will continue approximately every 12 weeks (+/- 3 weeks), or more frequently as needed, until death, withdrawal of consent, or the study closes, whichever is the earliest. This evaluation may be made by record review and/or telephone contact.

The final patient's last visit for the study will be defined as whichever of the following represents the last time point:

- When the last patient on study has completed their Safety follow-up visit, or
- When the last patient on study has documented toxicities to ABI-009 and nivolumab, and the toxicity has resolved, returned to baseline or is deemed irreversible after the Safety follow-up visit or
- When the last patient completes or discontinues the follow-up phase

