5.4. Follow-up Period for Survival and Initiation of Anticancer Therapy

Post-treatment survival time and any subsequent anticancer therapy information status will be monitored approximately every 12 weeks (+/-3 weeks) from EOT Visit or more frequently as needed, until death, withdrawal of consent, or the study closes, whichever is earliest. This evaluation may be by record review and/or telephone contact.

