8. STATISTICAL CONSIDERATIONS

8.1. Study Endpoints

Primary Endpoint:

- MTD

Secondary Endpoint(s):

- Disease control rate (DCR), ORR (CR+ PR)
- Progression-free survival
- Progression-free survival rate at 3,6,9,12 months
- Overall survival
- Incidence and grade of treatment-emergent AEs

Exploratory Endpoint(s):

- Correlation of response based on RECIST v1.1 and irRECIST
- Correlation between response and PD-L1 expression in patients' tumors
- Correlation between DCR and PTEN mutation in patient's archived tumor

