SAEs must be reported to AADI Drug Safety within 24 hours of the investigator's knowledge of the event by facsimile, or other appropriate method, using the SAE Report Form, or approved equivalent form.

The investigator's clinical judgment is used to determine whether a patient is to be removed from treatment due to an AE. The investigator is responsible for ensuring that all AEs observed by the investigator or reported by the patient that occur after the first dose of IP through the EOT Visit are reported using the applicable CRF (eg, Adverse Event Summary CRF).

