9.4. Serious Adverse Events

9.4.1. Definition of Serious Adverse Events

An SAE is defined as an AE that meets at least 1 of the following serious criteria:

- fatal
- life-threatening (places the patient at immediate risk of death)
- requires in-patient hospitalization or prolongation of existing hospitalization
- results in persistent or significant disability/incapacity
- congenital anomaly/birth defect
- other medically important serious event

An AE would meet the criterion of "requires hospitalization", if the event necessitated an in-patient admission to a health care facility (eg, overnight stay).

If an investigator considers an event to be clinically important, but it does not meet any of the serious criteria, the event could be classified as an SAE under the criterion of "other medically important serious event". Examples of such events could include allergic bronchospasm, convulsions, blood dyscrasias, drug-induced liver injury, or events that necessitate an emergency room visit, outpatient surgery, or urgent intervention.

Since the criteria for the CTCAE grading scale differs from the regulatory criteria for SAEs, if AEs correspond to grade 4 "life threatening" CTCAE grading scale criteria

(eg, laboratory abnormality reported as grade 4 without manifestation of life threatening status), it will be left to the investigator's judgment to also report these abnormalities as SAEs. For any AE that applies to this situation, comprehensive documentation of the event's severity status must be recorded in the patient's medical record.

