9.4.2. Reporting Procedures for Serious Adverse Events

All suspected unexpected serious adverse reactions (SUSARs) must be reported by the Investigator to their IRB in writing, and to the FDA within 7 days as required by law.

Any AE that meets any criterion for an SAE requires the completion of an SAE Report Form in addition to being recorded on the AE page/screen of the CRF. All SAEs must be reported to AADI Drug Safety within 24 hours of the investigator's knowledge of the event by facsimile, or other appropriate method, using the SAE Report Form, or approved equivalent form. This instruction pertains to initial SAE reports as well as any follow-up reports.

The investigator is required to ensure that the data on these forms is accurate and consistent. This requirement applies to all SAEs (regardless of relationship to IP) that occur during the study (from the time of signing of the informed consent form to 28 days after the last dose of IP), and those made known to the investigator at any time thereafter that are suspected of being related to IP.

The SAE report should provide a detailed description of the SAE and include a concise summary of hospital records and other relevant documents. If a patient died and an autopsy has been performed, copies of the autopsy report and death certificate are to be sent to AADI Drug Safety as soon as these become available. Any follow-up data will be detailed in a subsequent SAE Report Form, or approved equivalent form, and sent to AADI Drug Safety.

Where required by local legislation, the investigator is responsible for informing the IRB/EC of the SAE and providing them with all relevant initial and follow-up information about the event. The investigator must keep copies of all SAE information on file including correspondence with AADI and the IRB/EC.

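### New non-serious immune-mediated AEs that start after the 28-day window (at most the EOT Visit) have no planned route into the safety data

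*Combined protocol and SAP*

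**What the plan says.** **Recording window.** The Synopsis (Overview of Key Safety Assessments) says "All AEs will be recorded by the investigator from the time the patient signs informed consent until 28 days after the last dose of IP". Table 2 gives the same limit. Section 9.2 also gives 28 days, counted from the last dose of ABI-009, and then makes the investigator responsible for AEs "that occur after the first dose of IP through the EOT Visit are reported using the applicable CRF". The EOT Visit falls 4 weeks (± 7 days) after the last dose. The list of definitions counts this from the later of the two drugs.

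**After the window.** Section 9.4.2 adds SAEs, namely "those made known to the investigator at any time thereafter that are suspected of being related to IP". Section 9.4.1 lets the investigator class a clinically important event as serious, and drug-induced liver injury is one of its examples.

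**Follow-up contacts.** Section 5.4 reads: "Post-treatment survival time and any subsequent anticancer therapy information status will be monitored approximately every 12 weeks (+/-3 weeks) from EOT Visit". The contact may be by telephone or record review. No AE question is listed there or in Table 2.

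**Toxicity already known.** One of the conditions that can set the final patient's last visit in Section 2.5 is "When the last patient on study has documented toxicities to ABI-009 and nivolumab, and the toxicity has resolved". This follows events already on record and does not look for new ones.

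**Use of the data.** Section 8.1 lists "Incidence and grade of treatment-emergent AEs" as a secondary endpoint. Section 8.2 says that the study should give preliminary safety data for planning later studies.

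**The concern.** Section 1.3.3 warns: "Immune-mediated adverse reactions may occur after discontinuation of nivolumab therapy". In the trial it describes, 6 of 15 pneumonitis, colitis or hepatitis cases were diagnosed after nivolumab had been stopped. The collection rule here makes no allowance for this unless the event is serious. Grade 2 pneumonitis treated with steroids as an outpatient and first seen seven weeks after the last dose is an example: nobody is told to ask about it, and no form is planned for it.

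At stake is how completely the late immune toxicity of a new combination is described. Pneumonitis and hepatitis are of particular interest, because Section 7.6 gives dexamethasone on Day 8 specifically to reduce them. Dose escalation, the MTD and the efficacy endpoints do not depend on these events.

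**Working it through.** **1. Plan's own figures.** Section 1.3.3 gives immune-mediated pneumonitis 6/268 = 2.24% (stated 2.2%), colitis 6/268 = 2.24% (stated 2.2%) and hepatitis 3/268 = 1.12% (stated 1.1%). All three reproduce. The plan gives no expected number of late AEs.

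**2. Cases diagnosed after discontinuation (Section 1.3.3).** Pneumonitis 2 of 6, colitis 3 of 6, hepatitis 1 of 3: 6 of 15 in total. The interval from last dose to diagnosis is not given, so between 0 and 6 of them began after day 28.

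**3. Their grades.**
- Pneumonitis: 1 Grade 3 and 5 Grade 2 overall. The four on-treatment cases were all Grade 2, which leaves 1 Grade 3 and 1 Grade 2.
- Colitis: 5 Grade 3 and 1 Grade 2 overall. The three on-treatment cases are described as Grade 2 or 3, so the three later ones were most likely all Grade 3. On a looser reading, one was Grade 2.
- Hepatitis: 2 Grade 3 and 1 Grade 2 overall. Both Grade 3 patients restarted nivolumab, so the later case was most likely Grade 2.

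This gives 2 Grade 2 cases, or 3 on the looser reading of colitis.

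**4. Illustrative size.** Expected cases = N × k/268, and the chance of at least one = 1 − (1 − k/268)^N, with N = 40-50 from the Synopsis. All rows assume onset after day 28.

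| Counted as escaping | k | Rate | Expected cases | Chance of at least one |
|---|---|---|---|---|
| Grade 2 pneumonitis and hepatitis | 2 | 0.75% | 0.30-0.37 | 26-31% |
| Same, plus one Grade 2 colitis | 3 | 1.12% | 0.45-0.56 | 36-43% |
| Pneumonitis only (hepatitis reported as an SAE) | 1 | 0.37% | 0.15-0.19 | 14-17% |
| All six, any grade (none reported as an SAE) | 6 | 2.24% | 0.90-1.12 | 60-68% |

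If none began after day 28, every row is 0. For k = 2 the exact 95% CI is 0.09% to 2.67%, and its upper limit gives 40 × 0.0267 = 1.07 to 50 × 0.0267 = 1.33 cases.

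**5. What step 4 leaves out.** Section 1.3.3 reports Grade 1-2 hypothyroidism in 21/268 and hyperthyroidism in 8/268, together 29/268. It does not say how many started after discontinuation. If an assumed 5%, 10% or 20% began after the window, they would add 0.22-0.27, 0.43-0.54 or 0.87-1.08 cases. Other low-grade reactions cannot be quantified from the text.

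**6. Timing check.** A patient who stops for progression at the 6-week scan has had the last ABI-009 dose on Cycle 2 Day 15, which is day 36. The 28-day window closes on day 36 + 28 = 64, and the EOT Visit falls by day 36 + 35 = 71. The three cited hepatitis onsets were 86, 97 and 113 days after initiation. This shows only that such onsets can fall outside the window. It is not a rate, because those onsets include patients still on treatment.

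**7. First follow-up contact.** The EOT Visit is at 28 ± 7 days and the contact 84 ± 21 days later. That is 112 days after the last dose (range 21 + 63 = 84 to 35 + 105 = 140), or about 16 weeks (12-20).

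**The case against.** The strongest reply is that most of what matters is already caught. Related SAEs are taken in without a time limit, important events can be upgraded, and documented toxicity is followed. This is also a single center that may make contact more often than every 12 weeks. All of that stands and narrows the gap. It does not close it: upgrading is discretionary, and nothing in the plan asks for a new non-serious event.

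Second, treatment-emergent is not separately defined, so the recording window is in effect the boundary of the endpoint, and later events lie outside it. This is a fair point. It is a reason to show late events apart from the treatment-emergent tables, not a reason to leave them uncollected.

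Third, the numbers are weak. Grade is a poor stand-in for seriousness; Section 9.4.1 itself draws the distinction ("Since the criteria for the CTCAE grading scale differs from the regulatory criteria for SAEs"). The Grade 2 hepatitis case had high-dose steroids and persisted until death from progression, so it might well have been reported as serious. No cited case is shown to have begun after day 28. The rates come from nivolumab alone every 2 weeks, not from a 3-weekly combination with dexamethasone. These points stand, and the counts are therefore only an illustration.

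A reader might go further and infer that about 0.4 cases is a ceiling for everything missed, or that all six late diagnoses would have been lost. The documents support neither. The first leaves out thyroid, other low-grade and non-serious Grade 3 events. The second ignores the SAE route and the unstated interval.

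**Conclusion.** The gap is real but minor. A new immune-mediated AE that starts after the window and is not classed as serious has no planned route into the safety data, although the protocol acknowledges that such reactions occur. The study is descriptive, and no dose decision turns on these events.

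The number missed cannot be determined from the documents. The 0.30-0.37 cases in 40-50 patients apply to Grade 2 pneumonitis and hepatitis only. They rest on three assumptions: Grade 2 means not reported as serious, every post-discontinuation diagnosis began after day 28, and the cited monotherapy rate carries over. Relaxing the first two moves the figure down to 0.15-0.19 or to 0. Counting more event types moves it up, possibly to about one case or more.

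It would be wrong to read this as a loss of related serious events or as a threat to the MTD. This is a cheap improvement worth considering, not a defect that blocks the study.

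**What to change.** In Sections 5.4, 9.2 and 9.4.2 and in Table 2, add one item to the first scheduled 12-week follow-up contact (about 16 weeks after the last dose, range 12-20). Record any immune-mediated AE with onset since the EOT Visit that was clinically diagnosed or treated with steroids or hormone replacement, serious or not. Take the grade, onset date, relatedness and start date of any new anticancer therapy.

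In Section 8.2, report these events together with the late related SAEs on a separate line for onset more than 28 days after the last dose, apart from the treatment-emergent AE tables.

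The cost is one CRF item at an existing contact, one table line and some investigator time for grading and attribution. No visit or test is added. The limits should be stated: later therapy may confound attribution, grading rests on telephone or record review, and asymptomatic changes and events after that contact can still be missed (cited hypothyroidism onset runs to 11.7 months from initiation). Some patients may have died or changed treatment by then, since eligibility requires a life expectancy of only more than 3 months.
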